3.9.2 Adverse Event Data

When tabulating AE data, partial start dates will be handled as follows:

- If the year, month, and day are all missing, then set the onset day to the date of the first dose.
- If the month and day are missing, and the year is:
 - the same as the year of first dose, then set the onset day as the date of the first dose;
 - earlier than the year of first dose, then set the onset day as December 31;
 - after the year of the first dose, then set the onset day as January 1.
- If only the day is missing, then
 - if the month/year is the same as the first dose, then set the onset day as the date of first dose;
 - if the month/year is earlier than the month/year of the first dose, then set the onset day as the last day of the month;
 - if the month/year is later than the month/year of the first dose, then set the onset day as the first day of the month.

Partial end dates will only be imputed if the year is non-missing:

- If the month and day are missing, and the year is the same as the year of the last dose then set the end day as the last day of the month of the first dose. Otherwise, set the end date as December 31.
- If only the day is missing, then set the end day as the last day of the month.

If the imputed start date is later than the imputed end date then set the imputed start date to the imputed end date.

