1.3.1 Overview of Study Design

The study consists of three periods:

- **Period 1 – Induction (3 weeks):**

At the beginning of the 3-week induction period, eligible subjects will be randomized (2:1 ratio) to either TMB-001 0.05% once-a-day (QD) or Vehicle QD treatment, with use of mandatory standardized bland emollient (Cetaphil™) provided by the Sponsor.

- **Period 2 – Treatment (9 weeks):**

The dosing frequency in the 9-week treatment period will be increased in each treatment group to TMB-001 0.05% or Vehicle twice a day (BID). Mandatory bland emollient will be discontinued.

- **Period 3 – Maintenance (12 weeks):**

At Week 12, eligible subjects in the TMB-001 treatment group will be randomized (1:1 ratio) to open-label treatment with TMB-001 0.05% BID or QD. To be eligible, subjects must have achieved a \geq 1-point reduction in IGA score from Baseline.

Subjects with $<$ 1-point reduction in IGA score from Baseline will be discontinued from the study.

Vehicle-treated subjects who achieved $<$ 1-point reduction in IGA score from Baseline are eligible to cross over to the TMB-001 0.05% BID treatment group. Subjects with a \geq 1-point reduction in IGA score from Baseline will be discontinued from the study.

Subjects at the end of the study or subjects discontinued from the study at any time will be followed-up for an additional 2 weeks for the monitoring of adverse events.

Optional Maximal Use Arm

Adult and pediatric subjects, at a subset of preselected centers, will be enrolled in an open-label Optional Maximal Use arm to evaluate the systemic exposure and safety of topical TMB-001 0.05% ointment for the treatment of CI under maximal use conditions. Initially, adult CI subjects (\geq 17 years; n=16) and pediatric subjects (12-16 years; n=7-9) will be dosed for 14 days with TMB-001 0.05% BID. Following an interim PK analysis and based on the exposure data for subjects aged \geq 12 years, pediatric subjects aged 6 to 11 years (n=7-9) will begin dosing with TMB-001 0.05% BID for 14 days. Following the 14-day PK assessment period, subjects will receive TMB-001 0.05% BID treatment for 10 additional weeks to provide additional safety and limited efficacy data.

The schedule of assessments for both the Phase 3 study and the optional maximal use arm can be found in the study protocol.

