The total amount of study drug applied (in grams) will be summarized using descriptive statistics based on the data provided by the weighing of study drug tubes. A full – unused – tube's weight averages 101g. Any returned tube weighing more than 101g will be set to 101g. The assumption that the amount of study drug that was removed from the tube is equivalent to the amount of study drug applied will be used.

Additionally, actual dose intensity (g/day), defined as the ratio of total drug applied and the duration of study drug exposure will be summarized using descriptive statistics.

Data collected in the eDiary will be summarized using descriptive statistics, as applicable.

Specifically for Period 1 (the first 21 days), the number of Cetaphil applications per subject will be provided using descriptive statistics.

Both observed exposure data (including eDiary) and derived exposure parameters will be provided in by-subject data listings.

In addition to the Safety Population, all exposure analyses will be performed on the ITT population as well.

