7.2 Adverse Events

All adverse events (AEs) will be coded using the MedDRA v25.0 coding system and displayed in tables and data listings using system organ class (SOC) and preferred term. Missing and partial dates will be handled as described in Section 3.9.2.

Analyses of AEs will be performed for those events that are considered treatment-emergent, where treatment-emergent is defined as any AE with onset after the first application of study drug through 30 days after the last study drug application, or any event that was present at baseline but worsened in intensity or was subsequently considered drug-related through 30 days after the last study drug application.

Adverse events will be summarized by subject incidence rates; therefore, in any tabulation, a subject contributes only once to the count for a given AE in both SOC and preferred term. The table will be sorted by descending frequency, based on the overall column of the data presentation.

Adverse events will be reported separately by event type; reporting of SOCs and preferred term will be as described above.

The number and percentage of subjects with any treatment-emergent adverse event (TEAE), with any TEAE assessed as related to study drug (possibly or probably), with any serious TEAE, any non-serious TEAE, with any serious TEAE potentially related to study drug, any non-serious TEAE potentially related to study drug, with any common (occurring in $\geq 5\%$ of subjects) TEAE, or with any TEAE leading to study drug withdrawal will be provided. Additional tabulations will be provided for TEAEs by maximum severity, and TEAEs by strongest relationship to study drug.

All analyses above will be performed using both data presentations described in Section 3.9.3, where TEAEs will contribute to each summary only if they began in the corresponding period. For example, a TEAE starting during Periods 1 or 2 will be reported using the primary safety data presentation, and a TEAE starting during Period 3 will be reported using the open-label dosing data presentation.

Additionally, the proportion of subjects experiencing a TEAE through Week 12 will be reported along with exact binomial 95% confidence intervals, using the primary safety data presentation. The proportion of subjects experiencing a TEAE through Week 24 will be reported along with exact binomial 95% confidence intervals, using the open-label dosing data presentation.

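### The AE end-date rule in SAP 3.9.2 uses the month of the first dose, and with the start-after-end rule it can move some Period 3 onsets into the blinded-phase safety tables

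*SAP*

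**What the plan says.** SAP 3.9.2 sets the rules for partial AE dates. Four matter here.

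- End date with only a year: the rule applies when that year matches the year of the last dose. The value to impute is tied to the other end of treatment: "set the end day as the last day of the month of the first dose". In any other year the end becomes 31 December.
- Start date with the day missing: "if the month/year is later than the month/year of the first dose, then set the onset day as the first day of the month".
- Start date with only a year, where that year is "the same as the year of first dose, then set the onset day as the date of the first dose".
- Conflict between the two: "If the imputed start date is later than the imputed end date then set the imputed start date to the imputed end date".

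The imputed onset is then used in two places. SAP 7.2 assigns events to the blinded or open-label tables by onset: "TEAEs will contribute to each summary only if they began in the corresponding period". Section 6.0 of the SAP addendum ends a subject's time at risk at the onset of the first event of the type concerned.

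SAP 3.11.3 builds the primary safety columns on the initial randomization. SAP 1.3.1 lets vehicle subjects with less than a 1-point IGA improvement cross over to open-label TMB-001 BID. The addendum does not change 3.9.2 and states that SAP 3.0 otherwise still applies.

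**The concern.** The end-date rule tests the year against the last dose and then takes the month from the first dose. No reason is given, and it reads like a slip of one word. For an event that began well into treatment, the imputed end falls before the event started. The conflict rule then keeps that end and moves the start, overriding a month that the site recorded.

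Onset decides the table, so a moved onset puts the event in the wrong one. For a crossover subject, an event on open-label TMB-001 enters the Vehicle column of the blinded-phase table and raises the vehicle rate. For a subject on TMB-001 throughout, the event moves from the maintenance table to the TMB-001 column for Weeks 1 to 12 and raises that rate. The safety endpoint comparing TEAEs through Week 12 between TMB-001 and vehicle is exposed, as are the exposure-adjusted rates that the addendum adds at FDA request.

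**Working it through.** The plan gives no figure to reproduce, so the check applies the rules literally.

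**Inputs.** Day 1 is the date of first dose (SAP 3.2). Period 1 is Days 1–21 (SAP 7.1). Period 2 is the next 9 weeks, Days 22–84 (SAP 1.3.1). Treatment lasts 24 weeks (Protocol 4.2), so Period 3 is Days 85–168.

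**Example.** First dose 10 January 2023; last dose on Day 168, 26 June 2023; AE start recorded as May 2023, end as 2023.

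1. Start: day missing, month after the first-dose month, so 1 May 2023. That is 111 days after first dose, Day 112, Period 3.
2. End: year equals the last-dose year, so the end of the first-dose month, 31 January 2023.
3. The start is later than the end, so the start becomes 31 January 2023: 21 days after first dose, Day 22, Period 2.

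Time to onset loses 111 − 21 = 90 days. With first dose on 20 January 2023 the start moves from Day 102 to Day 12, which is Period 1.

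**Grid.** The rules were run for all 365 first-dose dates of a non-leap year and all 84 Period 3 onset days. Assumptions not in the documents: last dose on Day 168, events lasting 5 days, dates uniform. First and last dose fall in one calendar year for 198 of the 365 dates (first dose by 17 July).

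| Recorded start (end year-only) | Result |
|---|---|
| Day missing, dosing in one year | 52.1% move from Period 3 to 1, 30.2% from Period 3 to 2, 0.1% stay in Period 3; the other 17.6% already had a start imputed to Period 2 |
| Complete, dosing in one year | Onset never moves, but the imputed end precedes it in 99.9% |
| Year only, dosing in one year | The start rule already gives the first-dose date, so the end rule changes nothing |
| Day missing, dosing crosses a year end, first-dose year attached to the month | 46.5% move from Period 3 to 1, 21.3% from Period 3 to 2 |
| Day missing, dosing crosses a year end, recorded end year kept | None move |

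In the first row, onsets imputed to Period 3 make up 52.1 + 30.2 + 0.1 = 82.4%. Of these, 52.1/82.4 = 63% land in Period 1 and 30.2/82.4 = 37% in Period 2. Over 99% leave Period 3. Where an onset lands depends on the day of first dose: the end of the first-dose month lies within Days 1–21 for 252 of 365 dates (69%) and in Period 2 otherwise.

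When dosing crosses a year end and the first-dose year is attached, a year-only start in the later year (imputed to 1 January) can also move.

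**Size of one misfiled record.** With 110 subjects at 2:1, about 37 are on vehicle. One crossover event filed under Vehicle adds 1/37 = 2.7 percentage points to that event's incidence, if the subject had not already had it in the blinded phase. For the exposure-adjusted rates, 90/365 = 0.25 person-years are lost. If 110 subjects are followed for 12 to 24 weeks, the pooled total is 110 × 84/365 = 25 to 110 × 168/365 = 51 person-years, so the loss is about 1% to 0.5%, and a larger share within one arm.

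**After the correction.** With the month of the last dose, no onset in the grid leaves Period 3 and no imputed end precedes the true onset. The grid stops at Day 168, whereas the TEAE window in SAP 7.2 runs 30 days past the last application. In the example, a start of July 2023 becomes 1 July and the end 30 June, so the start would still be pulled back, by one day. The one-word change therefore does not remove the conflict by itself.

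**The case against.** The strongest reply is that this will rarely happen and will change little. Protocol 8.4 has sites ask about ongoing events at every post-baseline visit, so an end date known only to the year should be uncommon. Events with no recorded end year are not imputed, so ongoing events are untouched. SAP 7.2 plans no summary of AE duration or end date, so a wrong end date alone affects only listings. Misattribution to Vehicle is limited to vehicle subjects who crossed over. An onset that moves only between Periods 2 and 1 stays in the same table. No primary or key secondary efficacy analysis uses imputed AE dates. All of this stands, and it limits the size of the point.

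It can also be said that the intended rule is unknown, since SAP 3.9.3 uses 31 December for medications with the same missing parts. That is fair, and the sponsor should confirm the intent. But 31 December would not pull back a start in the same year either, so the parallel rule gives no support for the first-dose month.

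A reader might infer that Period 3 events in general are moved, or that they always land in Period 1. The documents do not support either. The conflict rule names only an imputed start, so complete starts stay put. The shift needs the date pattern described above. In the 10 January example the event lands on Day 22, in Period 2.

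**Conclusion.** The point holds within these limits. The rule is current text, nothing elsewhere in the SAP or addendum corrects it, and it can produce an onset that contradicts a recorded month. In the grid, with a day-missing start, a year-only end and dosing in one calendar year, nearly every onset imputed to Period 3 goes to the blinded-phase tables. For dosing that crosses a year end, the result depends on which year is attached to the first-dose month, and the SAP does not say.

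The percentages rest on the uniform-date, full-course and 5-day assumptions. They describe what happens to a record with this pattern, not how many such records exist; the documents give no count, and it is probably small. The effect is confined to safety tables and exposure-adjusted rates. It is a minor error in scale, but worth correcting before the AE tables are run, because it can credit an event on active drug to Vehicle.

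**What to change.** Make two changes in SAP 3.9.2.

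1. In the year-only end-date rule, replace the first dose with the last dose as the source of the imputed month, and state that the recorded end year is kept.
2. Replace the conflict rule where the start month and year are recorded: keep the start, and set the imputed end no earlier than the last day of the onset month, or the onset date if the start is complete. This also covers events starting after the last-dose month but within the 30-day TEAE window.

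The cost is one word and one or two clauses, plus the matching program change. If the AE tables have already been run, list the records with a year-only end in the last-dose year, check which onsets moved, and rerun the affected tables.

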3.9.3 Prior and Concomitant Medication Data

When tabulating prior/concomitant medication data, partial start dates will be handled as follows:

- If the year, month, and day are all missing, then set the start date to the date of first dose.
- If the month and day are missing and the year is earlier than the year of the first dose, then set the start date to December 31. Otherwise, set the start date to the date of first dose.
- If only the day is missing, if the month/year is earlier than the month/year of the first dose then set the start date to the first day of the month. Otherwise, set the start date to the last day of the month.

Partial end dates will only be imputed if the year is non-missing:

- If the month and day are missing then set the end date to December 31.
- If only the day is missing, then set the end day as the last day of the month.

If the imputed start date is later than the imputed end date then set the imputed start date to the imputed end date.

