5.1.1 Estimand

The primary estimand is defined by the following:

- Population: Subjects in the ITT population as defined by protocol eligibility criteria.
- Variable: the proportion of subjects with a ≥ 2 -point improvement in the IGA score at Week 12 compared to baseline.
- The following intercurrent events and their handling include:
 - Treatment discontinuation prior to Week 12 due to adverse event or lack of efficacy: Composite variable strategy, where the discontinuation may be considered informative about the subject's outcome and will therefore consider these subjects as non-responders.
 - Modification to dose level: Treatment policy strategy, where results will be used regardless of dose modifications.
 - Use of prohibited medication: Composite variable strategy, where the use of such medication may be considered informative about the subject's outcome (e.g., subjects are using prohibited medications due to perceived lack of efficacy of study drug) and will therefore consider these subjects as non-responders.
- Population-level summary: The difference in proportions of subjects achieving IGA response at Week 12 between treatment groups (TMB-001 0.05% and vehicle).

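### SAP 3.9.3 dates a medication start known only by a later year to the first-dose day, contradicting the recorded year; any effect on response is conditional and small

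*SAP*

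**What the plan says.** SAP 3.9.3 opens with "When tabulating prior/concomitant medication data, partial start dates will be handled as follows". For a start date with month and day missing it has two branches. The first applies "If the month and day are missing and the year is earlier than the year of the first dose" and gives 31 December. The second is "Otherwise, set the start date to the date of first dose". The section closes with a consistency step: "If the imputed start date is later than the imputed end date then set the imputed start date to the imputed end date".

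SAP 3.9.2 deals with the same pattern for adverse events in three branches. The same year as first dose gives the first-dose date, an earlier year gives 31 December, and the third reads "after the year of the first dose, then set the onset day as January 1".

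SAP 5.1.1 lists "Use of prohibited medication: Composite variable strategy" among the intercurrent events of the primary estimand; for that event the plan "will therefore consider these subjects as non-responders". No time limit is written for it. The other composite event does carry one: "Treatment discontinuation prior to Week 12 due to adverse event or lack of efficacy". SAP 5.2.1 and 5.3.1 apply the same strategy to the key and other secondary endpoints.

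SAP 7.6 sends missing and partial medication dates to 3.9.3, and separates prior from concomitant medication by whether the drug ended before the first application. The SAP addendum does not amend 3.9.3.

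**The concern.** With only the year known, the second branch of 3.9.3 collects two different cases: a start in the first-dose year and a start in a later year. In the first case the first-dose date is a possible, cautious choice. In the second it cannot be right, because the imputed date lies in a year before the recorded one. The later-year branch present in 3.9.2 is missing here and no reason is given, so this reads as an omission rather than a choice.

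What could be at stake is the prohibited-medication rule. Protocol Table 1 schedules concomitant medication at every visit up to Visit 9 (Day 168), so drugs started in the open-label maintenance period sit in the same data as those started in the double-blind period. If imputed start dates decide whether prohibited use occurred by Week 12, a drug that can only have begun after Week 12 would be counted on the first-dose day, and a Week 12 responder would be analysed as a failure.

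**Working it through.** The plan states no figure on this point, so there is none to reproduce. The check applies both date rules to the same record.

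**Inputs.** Week 12 is Day 84 and Week 24 is Day 168, with baseline as Day 0 (Protocol Table 1). The total is 110 subjects randomized 2:1 (SAP 1.3.2 and 1.3.3). The documents give no first-dose dates, so the calendar dates below are illustrations.

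**Step 1: the rules side by side (month and day missing).**

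| Recorded year | SAP 3.9.3, medications | SAP 3.9.2, adverse events |
|---|---|---|
| Before first-dose year | 31 December | 31 December |
| Same as first-dose year | First-dose date | First-dose date |
| After first-dose year | First-dose date | 1 January |

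The rules differ only in the last row. Applied to all 365 possible first-dose dates, with a recorded year one later, the medication rule returns the wrong year every time.

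**Step 2: does the closing step repair it?** No. It acts only when the start is later than the end. A start on the first-dose date always precedes an end date in a later year.

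**Step 3: which outputs use the date?** Prior/concomitant status depends on the end date, and the ATC and preferred-term tables count subjects by drug. Neither changes. Only a use that times the start of a drug can be affected.

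**Step 4: when would Week 12 status change?** Suppose that imputed starts time the prohibited-medication event and that only use up to Week 12 counts. Take a drug recorded only by the year after first dose.

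- For treatment to reach 1 January, first dose + 168 days must be on or after 1 January. This holds for first doses from 17 July to 31 December: 168 of 365 dates.
- For the recorded year to prove a start after Week 12, 1 January must be later than first dose + 84 days. This holds for first doses from 17 July to 8 October: 84 of the 168.
- For the other 84 (9 October to 31 December), 1 January is on or before Day 84. The 3.9.2-type rule would still place the drug within the first 12 weeks, so the classification stays the same under either rule.

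These limits are approximate, because Visits 6 and 9 each have a window of ±7 days.

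**Step 5: an example.** First dose 1 September 2022; Week 12 = 1 September + 84 days = 24 November 2022. A prohibited drug is recorded as started in 2023.

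- Rule in 3.9.3: 1 September 2022, so counted before Week 12.
- Rule as in 3.9.2: 1 January 2023, which is 122 days after first dose and after Week 12, so not counted.

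**Step 6: which arm, and how much?** A vehicle subject with at least a 1-point IGA reduction is discontinued at Week 12 (SAP 1.3.1). Every vehicle responder on the primary endpoint (at least 2 points) therefore leaves then. Concomitant medication is not scheduled at the Visit 10 safety follow-up, so such a subject has no scheduled Period 3 record to misdate. TMB-001 responders may continue to Week 24. For the primary endpoint only the TMB-001 rate can change, and only downwards: 110 × 2/3 ≈ 73 subjects, and 1/73 ≈ 1.4 percentage points per subject.

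**The case against.** The strongest reply is that the rule may never touch an efficacy result. It is introduced for tabulation, and the tables it serves do not depend on the start date. SAP 5.1.1 does not cite it and sets no window for prohibited medication; if use at any time counted, the imputed date would be irrelevant. The trigger should also be rare. Protocol 6.5 asks for start and end dates of every medication, and in Period 3 the visits that review medication are nominally four weeks apart. What is needed is a prohibited drug, with only its year recorded, begun after Week 12 and after a year end, in a Week 12 responder. Any error then works against TMB-001.

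All of this stands as a limit on consequence. It does not rescue the rule: the date is false for every later-year record, and 3.9.3 is the only medication date rule that a programmer would find in the SAP.

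Three stronger readings are tempting and not supported.

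- A reader might take the share of subjects whose treatment crosses 1 January under uniform enrolment (168/365, 46%, for 24 weeks; 84/365, 23%, for 12 weeks) as the share affected. These count subjects with a possible calendar overlap, not faulty records. Moreover, subjects whose first 12 weeks cross the year end are those for whom the correction leaves Week 12 status unchanged.
- A reader might expect a November first dose to show the harm. It shows the impossible date, but not a changed outcome: with first dose on 1 November 2022, Week 12 is 24 January 2023, and 1 January still falls before it.
- A reader might assign a similar loss to vehicle, 1/37 or 2.7 points per subject. For the primary endpoint this cannot arise from Period 3 records, because vehicle responders have left.

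**Conclusion.** Wrong as written, minor. That 3.9.3 gives a date contradicting the recorded year follows from the text and needs no assumption.

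An effect on the primary result rests on two assumptions that the SAP neither states nor rules out: that 3.9.3 dates are used to time the prohibited-medication event, and that the event is confined to use up to Week 12. If both hold, each affected subject moves the TMB-001 response rate down by about 1.4 points, only for first doses from about 17 July to 8 October. The documents do not allow the number of such subjects to be estimated; it is probably very small. They do not support saying that responders will be lost, or that efficacy could be overstated on the primary endpoint by this route.

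**What to change.** In SAP 3.9.3, split the second branch for month and day missing. Keep the first-dose date when the recorded year is the first-dose year, and set the start to 1 January of the recorded year when it is later, as 3.9.2 does.

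In SAP 5.1.1, state the period in which prohibited-medication use counts for the Week 12 endpoints, and whether recorded or imputed dates decide it. Carry the same statement to 5.2.1 and 5.3.1, with the period adapted for the Week 24 endpoints. The first change alone leaves open whether the date rule reaches the endpoint at all.

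The cost is one line in 3.9.3, a sentence or two in 5.1.1 with matching references, and a small change to the date derivation. No new data are needed.
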